Protocol and statistical plan

Validity and Reliability of the 6-minute Walk Test Over a Distance of 6 Metres in People With Multiple Sclerosis

NCT number: 04228328

10 January 2020

Protocol and statistical plan

Sponsor / Sponsor-Investigator	Pr [name], Professeur HES associé, [name], t : [contact], [contact]
Study Title	Validity and Reliability of the 6-minute Walk Test Over a Distance of 6 Metres in People With Multiple Sclerosis
Short Title / Study ID	VTM6M6m, CERVD-2019-01864
Study Registration	Clinicaltrial.gov : NCT04228328 Swiss National Clinical Trial Portal : SNCTP000003657
Study Category and Rationale	
Minimum risks (A category)
 
The tests are current and usual tests in the normal care of people with multiple sclerosis. Participants only have to walk for 6 minutes and to turn around. This turn will be timed.

Background and Rationale	The 6-minute walk test is used by physiotherapists to monitor the walking endurance of patients with multiple sclerosis. The protocol for this test calls for a distance of 30 meters (6MWT30) to be walked. However, this distance is not always available in practices and at patients' homes. The aim of this study is to validate a shorter version over a distance of 6 meters (6MWT6) and to evaluate its intra-rater reliability and the reliability of the instrument.
Risk / Benefit Assessment	
The risks are a temporary increase in fatigue and the risk of falling.
 
The direct benefits go beyond the knowledge of the performance of the tests. The participants will have feedback on their walking abilities and will use these data for their physiotherapeutic follow-up. Performing the tests will contribute to their training in walking and physical activity recommended in their situation.
 
The indirect benefits are the satisfaction of being able to help research on the disease that impacts them directly. Indeed, if there is a good correlation and concordance between the 6MWT6 and the 6MWT30, the use of the 6-minute test over 6 meters could be generalized.

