Objective(s)	
The main objective is to validate a different version of the 6MWT, the 6MWT6.
 
The secondary objectives are to verify the reliability of this new version (of the instrument and of the rater) and to analyze the possible differences between the 6MWT6 and the 6MWT30 (according to the speed at the half-turn and other parameters: age, gender, height, EDSS score, type of disease, time since last relapse)

Endpoint(s)	
6-minute walk test over 6 meters: meters walked
 
6-minute walk test over 30 meters: meters walked
 
360 Degree Turn Test: time in seconds and number of steps

Study Design	Non-randomized validation study
Statistical Considerations	The primary objective is to validate a new version of the 6MWT over a distance of 6 m, so it is necessary to prove that there is an excellent correlation with the 6MWT30, the current reference. To do this, the data will be first presented, as means and standard deviations for normally distributed variables, and as medians and interquartile ranges for non-normally distributed variables. The differences between the 6MWT6 and 6MWT30 will be

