	
plotted (absolute and relative values) and a test of comparison of means will be performed with Student's ttest.
 
Than, a Pearson or Kendall coefficient (depending on the distribution of the data) will be used. Analysis of the degree of agreement according to the method described by Taffé (bias and precision plot) will supplement the Bland and Altmann plot (Taffé, 2018; Taffé et al., 2020).
 
The secondary objective, reliability, will be assessed using the Intra Class Coefficient (ICC), according to the model: two-way mixed-effects as recommended by Koo (2016), as repeated measures cannot be considered as random sampling and absolute agreement, as agreement between repeated measures is sought (Koo & Li, 2016). The 6MWT6 data at Day1 will be compared to the same data at Day2 to assess intrarater reliability. These data will be compared to the post hoc count based on the video performed at Day1 and Day2 for instrument reliability.
 
For the last objective, analysis of explanatory factors for the differences between 6MWT6 and 6MWT30, correlation analyses will be performed between the continuous variable of these differences and the 360DTT. Multiple linear regressions will then be performed between this dependent variable "6MWT30 - 6MWT6" and the continuous and categorical variables: 360 DTT (time), age, gender, height, time since last relapse, type of MS, and assistive device. All analyses will be performed using STATA software, v.15.1. (StataCorp LLC, College Station, TX, USA).

Inclusion- / Exclusion Criteria	
The project focuses on the population of walking patients with MS.
 
Inclusion: adults, confirmed diagnosis of MS, Expanded Disability Status Scale (EDSS) score 3 to 6.5, or be able to walk 30 metres with or without aids, good understanding of French, have already completed a 6-minute walking test, be able to give consent by signature.
 
Exclusion: Lung disease, heart disease, co-morbidity preventing 6minWT, relapse in the last 3 months, chronic fatigue \geq at 8 (Visual Analog Score-Fatigue).

Number of Participants with Rationale	21 participants will be needed to obtain a good correlation coefficient, which is the objective of the validation of the new version of the 6MWT. The alpha was set at 0.01, the power at 0.9 for a correlation of 0.8
Study Intervention	Test under study: People have to walk for 6 minutes without stopping when possible.
Control Intervention	No control intervention.

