Study procedures	Eligible patients will be recruited by their treating physiotherapist or through the presentation of the project to the regional groups of the Swiss MS Society. The patients will be interns at the Institution or will come to the Institution of Lavigny for 2 times 1 hour and 20 minutes of testing at one week intervals. On the first day (Day1), they will perform the 6MWT6, followed by a 15-45 minutes lying down break, then they will perform the 360 Degree Turn Test. On the second day (Day2), they will perform the 6MWT30 and then the 6MWT6, interspersed with a 15-45 minutes break.
Study Duration and Schedule	March to November 2020
Investigator(s)	[name], physical therapist Bsc, student in Master of Sciences. 21 years of experience with multiple sclerosis patients
Study Center(s)	Insitution de Lavigny, [name] Tél. [name] Switzerland

Ethical consideration	
1. The results of this study would be generalized to the population of MS walkers with an EDSS between 3 and 6.5. They will allow the use of a valuable tool, the 6MWT6, in previously impossible contexts, i.e. in the practices and at patients' homes. Participants will benefit directly from feedback on their abilities, be able to compare these results to previous results and use this data for their physiotherapeutic follow-up. Performing the tests will contribute to their training in walking and in the physical activity recommended for their situation. The indirect benefits are the satisfaction of being able to help research on the disease that impacts them directly. The main risk is a temporary increase in fatigue.
 
2. The proposed methodology is ethical because, in order to evaluate the reliability and validity of a test, while excluding the fatigue bias, it would be necessary to call the patient 3 times at a few days interval. In this context, it was attempted to do it in 2 days rather than 3 and the impact of fatigue was minimized through the systematization of the breaks in lying position with adjustable duration according to the patient's condition.

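### One fixed test order and an unnamed 6MWT6 leave the mean difference between the 6 m and 30 m courses inseparable from order or session effects

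*Combined protocol and SAP*

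**What the plan says.** Under Study procedures, all participants follow one sequence over two visits a week apart. "On the first day (Day1), they will perform the 6MWT6, followed by a 15-45 minutes lying down break" and then the 360 Degree Turn Test. At the second visit "On the second day (Day2), they will perform the 6MWT30 and then the 6MWT6, interspersed with a 15-45 minutes break". The Study Design row describes the study as non-randomized, and nothing in the document varies the order.

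Under Statistical Considerations, the primary aim is correlation: "it is necessary to prove that there is an excellent correlation with the 6MWT30, the current reference". The plan also plots the differences between the two courses, and "a test of comparison of means will be performed" with Student's t-test. It adds Bland-Altman and Taffé bias-and-precision analyses and a multiple regression with 6MWT30 − 6MWT6 as the outcome. None of these says whether the Day 1 or the Day 2 6MWT6 is used. Days are named only for reliability: "The 6MWT6 data at Day1 will be compared to the same data at Day2 to assess intrarater reliability", together with the video count from both days. The regression covariates include neither order nor session.

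The plan does recognise fatigue. Ethical consideration, item 2, says that to assess reliability and validity "while excluding the fatigue bias, it would be necessary to call the patient 3 times", and explains that two visits with lying breaks of adjustable length were chosen instead. Participants must also "have already completed a 6-minute walking test", and people with a recent relapse or a fatigue score of 8 or more are excluded.

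**The concern.** On Day 2 the 6MWT6 is always the second walk. If a second walk is shorter because of fatigue, or longer because of practice, the Day 2 difference contains that change. The Day 1 6MWT6 is, like the 6MWT30, the first walk of its day, so within-day order drops out, but the two are a week apart and any session effect enters. Leaving the pair unnamed also leaves the choice open until the data have been seen.

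The mean difference matters because the Risk / Benefit Assessment makes wider use of the short course conditional: "if there is a good correlation and concordance between the 6MWT6 and the 6MWT30". Concordance depends on the mean bias as well as on correlation. A shift would displace the t-test, the centre of the Bland-Altman plot, the Taffé bias estimate and the regression intercept. It could create an apparent bias of the 6 m course or hide a real one.

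**Working it through.** **Inputs.** From the document: the three walks and their order, the one-week interval, n = 21, and alpha 0.01 (stated for the sample size only; none is given for the t-test). The plan gives no order effect, SD of differences or between-person SD, so it has no figure of its own to reproduce on this point, and every size below is an assumption. I take n = 21 as given; whether its derivation reproduces is a separate matter. I treat the t-test as paired and two-sided, which the plan does not state.

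**1. What each contrast estimates.** Let C be the effect of the 30 m course relative to the 6 m course, S the effect of the second session, P the effect of walking second within a day, and μ the mean. The expected distances are:

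- Day 1 6MWT6: μ
- Day 2 6MWT30: μ + C + S
- Day 2 6MWT6: μ + S + P

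Hence:

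- 6MWT30 − Day 1 6MWT6 = C + S
- 6MWT30 − Day 2 6MWT6 = C − P
- 6MWT30 − mean of both 6MWT6 = C + (S − P)/2
- Day 2 6MWT6 − Day 1 6MWT6 = S + P

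Three cell means serve four parameters: the design matrix has rank 3 of 4, and C is not estimable. If some participants walk the 6MWT6 first on Day 2, the rank is 4 and C is estimable.

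**2. How often order or session alone would look like a course effect.** Set C = 0 and let the net shift be δ, with SD of the paired differences σ. The rejection probability is that of a noncentral t with 20 degrees of freedom and noncentrality (δ/σ)√21.

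| Shift | SD 20 m | SD 30 m | SD 40 m |
|---|---|---|---|
| 10 m, alpha 0.05 | 0.59 | 0.31 | 0.19 |
| 15 m, alpha 0.05 | 0.90 | 0.59 | 0.37 |
| 20 m, alpha 0.05 | 0.99 | 0.83 | 0.59 |
| 10 m, alpha 0.01 | 0.32 | 0.12 | 0.06 |
| 15 m, alpha 0.01 | 0.72 | 0.32 | 0.16 |
| 20 m, alpha 0.01 | 0.95 | 0.59 | 0.32 |

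**3. Correlation, limits of agreement and ICC.** Assume between-person SD 80 m (variance 6400) and error SD 25 m (variance 625).

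- Constant shift: r = 6400/7025 = 0.911 and limits of ±1.96√(2 × 625) = ±69 m around the mean difference. Neither depends on the shift.
- Fatigue varying between people with SD f: r = 6400/√(7025 × (7025 + f²)) = 0.905, 0.897 and 0.886 for f = 10, 15 and 20 m. The limits, ±1.96√(1250 + f²), become ±72, ±75 and ±80 m.
- Absolute-agreement ICC, Day 1 against Day 2, with a 20 m shift: 6400/(7025 + 20²/2) = 0.886 instead of 0.911.

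**4. Randomised Day 2 order, 11/10.**

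- With an order term, C is estimated by the average of the two sequence means, with variance σ² × ¼(1/11 + 1/10) = 0.04773σ², against σ²/21 = 0.04762σ² unadjusted. At σ = 30 m the 95% half-width is 2.093 × 30 × √0.04773 = 13.72 m, against 2.086 × 30/√21 = 13.66 m.
- In simulation (40,000 runs per setting, shifts 10-20 m, SD 20-40 m) the mean bias was within 0.1 m. Rejection was 4.8-5.1% at 0.05 and 1.0-1.1% at 0.01.
- Without adjustment, mixing the orders adds variance v = (11/21)(10/21) × 20² = 99.8 for a 20 m shift. The raw correlation is then (6400 − 99.8)/(7025 + 99.8) = 0.884, and the limits are ±1.96√(1250 + 4 × 99.8) = ±80 m. Order adjustment returns these to about 0.911 and ±69 m.

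**The case against.** The strongest reply is that the stated criterion is correlation. The sample size rests on it, and a constant shift does not move it. Even fatigue varying between people leaves r at 0.886 or above in the examples, still above the planned 0.8. No margin or decision rule is attached to the mean difference. This stands, and it limits the weight of the point. It does not remove it, because the plan itself estimates the mean bias and ties wider use to concordance.

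Second, the rejection rates assume no true course effect, although a 6 m course has five times as many turns per metre (30/6) and the plan expects differences. That is fair: the rates show how readily order passes for course, and do not predict the result. With a real course effect the same shift still biases the estimate.

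Third, the Day 1 pair identifies the course effect if there is no session effect, which is plausible in relapse-free people who know the test. The planned Day 1 against Day 2 6MWT6 comparison also offers a check. But the plan neither names that pair nor states the assumption, and the check gives only S + P, in which opposite effects can cancel.

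Fourth, the fatigue compromise is disclosed. It explains two visits rather than three, but not why the Day 2 order is the same for everyone.

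Fifth, randomising has a price for the unadjusted analyses, as shown above, and the adjustment is imprecise. In the same scenario the order effect has standard error √1250 × √0.04773 = 7.7 m, so a true 20 m would be estimated anywhere from about 5 to 35 m. If walking second changes the 6MWT30 by a and the 6MWT6 by b, a bias of (a − b)/2 remains. These costs are real and belong in the plan.

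**Conclusion.** The concern holds. The order is fixed, the comparison pair is unnamed, and no planned contrast isolates the mean course effect without assuming that session or within-day order has no effect. Lying breaks, earlier test experience and the exclusions may shrink those effects but do not let the study estimate or remove them.

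The structural finding needs no numerical assumption. Its size does: for shifts of 10-20 m and SDs of 20-40 m, order or session alone would be significant in 19-99% of studies at 0.05 and 6-95% at 0.01. The direction and size of any actual shift cannot be learned from the documents. The effect on the ICC is small. Under a constant shift the correlation, the regression slopes and the width of the limits of agreement are unaffected. This should be fixed, but it does not undermine the correlation analysis.

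**What to change.** 1. Name the Day 2 same-day pair as the validity comparison throughout Statistical Considerations, and keep the Day 1 6MWT6 for reliability.
2. Randomise the Day 2 order: 11 participants with the 6MWT30 first, 10 with the 6MWT6 first.
3. Estimate the mean course difference with an order term. State that this assumes the same order effect on both courses, which 21 people can test only weakly.
4. Report the correlation, Bland-Altman and Taffé analyses on order-adjusted as well as raw values, and define the adjustment in advance (for example, subtracting the estimated order effect from each second-walk distance). An order term in the mean-difference model alone does not correct these analyses.
5. For reliability, include Day 2 order as a model term rather than splitting into subgroups of 10 and 11.

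The cost is an allocation list, one model term, one degree of freedom and an edit to the Study Design row. Visits, tests, breaks and staff are unchanged. About half of the 6MWT30 tests would be done second, and the raw correlation and limits would look somewhat worse if there is an order effect.

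If the fixed order is kept, still name the pair and report the mean difference as course plus order (Day 2 pair) or course plus session (Day 1 pair), not as bias of the 6 m course. Show the Day 2 minus Day 1 6MWT6 difference beside it as a partial check. This costs almost nothing.
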